B. Study Type and Design: This study is a longitudinal, repeated measures, double-blinded design with subjects randomly assigned to placebo, low (20 mg/d) or high (80 mg/d) atorvastatin therapy during a 12-week aerobic exercise training protocol. We expect to screen approximately 150 participants to enroll (randomize) a maximum of 80 participants. The overall goal is to have 60 participants complete all study procedures (20 in each group). Repeated measures design allows each subject to serve as their own control. Placebo groups are included to account for potential changes in muscle mitochondrial function independent of statin therapy over the 1 year dose-response.

C. Sample size, statistical methods, and power calculation: The randomization for study drugs will be carried out by the biostatistician using a computer-based random number generator at a 1:1:1 allocation. Sample size for the study is powered on the basis of detecting a difference in VO₂peak between the EX+Plac group and the EX+Atorva80 group as well as between the EX+Atorva20 group and the EX+Atorva80 group at 12 weeks post-treatment. In our previously published study(13) (Table 2) the EX only group had a mean 2.6 ml/kg/min increase in VO₂peak following 12 weeks of training while the EX+Statin group only had a 0.4 ml/kg/min increase in VO₂peak. The estimated effect size of between group differences is 0.9 (Cohen's d). The increase of VO₂peak in the EX+Atorva20 group is expected

to be similar to that of EX+Plac group. A sample size of 35 per group provides 80% of power of detecting an effect size of 0.75 for a two-sided, two-sample t-test at 0.025 levels. Here, we use 0.025 for each group comparison to maintain the overall type I error rate at 0.05 level using Bonferroni correction. Assuming variances similar to what was observed in the pilot study, this study is powered to detect a difference of 1.53 ml/kg/min VO₂peak between groups. These power calculations led to a desired final sample size of 105 (35/group). We plan an enrollment of 120 (40/group) subjects to account for 10% dropout rate. The subject enrollment will be split equally between the two sites. As an exploratory analysis, the mean difference of VO₂peak (EX+ Atorva20- EX+ placebo) and its 95% confidence interval (CI) will be estimated. If the lower bound of the 95% confidence interval is greater than -0.8 ml/kg/min, EX+ Atorva20 will be considered non-inferior to EX+ placebo.

D. Subject Criteria

[figure not shown]

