- E. Quality Assurance / Monitoring:** Data will be reviewed twice a year by the Board Chair. In addition, data will be reviewed on a yearly basis with the biostatistician, [name] to determine if the studies should be shortened due to either no measured effect or due to effects that are greater than what power calculations indicated. The PI and other key personnel will be examining research data on a subject to subject basis to ensure it is accurate and to address any potential problems that may arise with the protocols. In addition, Drs. [name] and [name] will discuss data at least once per month through in person meetings or by phone to ensure that data collection is occurring in a consistent manner at both locations.

V. Data Analysis and Reporting

- A. Statistical and Data Analysis:** This project is a two-factor study. One factor is treatment group (between subjects) and a second factor is time of data collection (0, 1, 6, and 12 months) (within subject). The data analysis will be carried out for the primary outcome variable of cardiorespiratory fitness, in addition to other outcome variables (muscle mitochondrial change, and insulin sensitivity, etc.). For each measure, its baseline measure and age will be added as covariates to adjust for the individual difference at baseline. Two-way interaction between treatment and time will be added in the model for testing if the outcome changes differently between groups over time. Additional variables, such as demographics, BMI, physical activity, etc. may also be included as covariates. If the test of trend difference is significant, then the comparison at each time point will also be considered to identify when the difference between groups reaches the maximum. Least Square Means will be used for the aforementioned comparisons. The statistical analysis will be performed with mixed procedure in STATA 13.1 (StataCorp LP, College Station, TX). Mixed model does

not require complete data for a longitudinal study. Residual analyses will be conducted and efforts to address those will be made, including appropriate transformations.

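### The pilot effect (2.2 ml/kg/min, d = 0.9) and the stated detectable difference (1.53 ml/kg/min at d = 0.75) in section II.C imply different SDs, so 0.9 and 1.53 cannot both stand as written

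*Combined protocol and SAP*

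**What the plan says.** All the figures are in one paragraph of the protocol, section II.C (sample size, statistical methods and power calculation).

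- Pilot gains in VO₂peak over 12 weeks: "the EX only group had a mean 2.6 ml/kg/min increase", while "the EX+Statin group only had a 0.4 ml/kg/min increase".
- Pilot effect size: "The estimated effect size of between group differences is 0.9", identified as Cohen's d.
- Sizing: "A sample size of 35 per group provides 80% of power of detecting an effect size of 0.75", for a two-sided two-sample t-test at 0.025 per comparison (Bonferroni over two comparisons).
- Conversion to clinical units: "Assuming variances similar to what was observed in the pilot study", "this study is powered to detect a difference of 1.53 ml/kg/min".

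No SD is given in numbers. Sections II.K.b and IV.E also provide for a yearly data review that may shorten the study, among other reasons "due to effects that are greater than what power calculations indicated".

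**The concern.** Cohen's d is a difference divided by an SD. If the pilot d and the detectable difference both use the pilot SD, as the paragraph reads, then 1.53 must stand to 2.2 as 0.75 stands to 0.9. It does not.

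The 1.53 is the only detectable difference that the plan gives in ml/kg/min for its primary outcome. It is the figure a reader would use to judge whether a null result excludes an effect that matters. If d = 0.9 is correct, the plan claims 80% power for a smaller effect than 35 per group can deliver. The yearly review is a lesser matter. Its wording names no unit or figure, but if the benchmark is taken from II.C in ml/kg/min, it is either 1.53 or about 1.83, depending on which figure is corrected.

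**Working it through.** **Inputs.** From II.C: gains of 2.6 and 0.4, d = 0.9, sizing effect 0.75, 35 per group, two-sided alpha 0.025, 80% power, detectable difference 1.53. Table 1 in section I.C confirms the gains: 29.5 − 26.9 = 2.6 and 26.5 − 26.1 = 0.4. The pilot difference is 2.6 − 0.4 = 2.2 ml/kg/min.

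**The plan's sample size reproduces.** For a two-sample t-test (noncentral t) with d = 0.75 and two-sided alpha 0.025, 35 per group gives 79.9% power. Solving for 80% gives 35.08 per group. The 0.75 and the 35 are therefore sound, and the 2.2 is confirmed by Table 1. That leaves 0.9 and 1.53.

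**Check that needs no SD.** On one SD, 1.53/2.2 must equal 0.75/0.9.

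| Ratio | As printed | With every figure at its rounding limits |
|---|---|---|
| 1.53/2.2 | 0.695 | 1.525/2.3 to 1.535/2.1 = 0.663 to 0.731 |
| 0.75/0.9 | 0.833 | 0.745/0.95 to 0.755/0.85 = 0.784 to 0.888 |

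The ranges do not overlap, so rounding is not the explanation.

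**If d = 0.9 is right.**
- SD = 2.2/0.9 = 2.44 (2.1/0.95 = 2.21 to 2.3/0.85 = 2.71).
- Detectable difference = 0.75 × 2.44 = 1.83 ml/kg/min (0.75 × 2.21 = 1.66 to 0.75 × 2.71 = 2.03).
- 1.53 is then d = 1.53/2.44 = 0.63 (0.57 to 0.69). Power at 35 per group, two-sided 0.025, is 63% (53% to 73%). Reaching 80% for 1.53 would take about 50 per group.

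**If 1.53 is right.**
- SD = 1.53/0.75 = 2.04.
- Pilot d = 2.2/2.04 = 1.08 (1.02 to 1.14 with rounding), not 0.9.
- Power for 1.53 is 80%, as stated.

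**Power for the full pilot difference of 2.2 at 35 per group.** It is 93% with d = 0.9 and 99% with d = 1.08.

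**Can Table 1 settle it?** No. Its ± values are not labelled as SD or SE, and they describe pre and post levels, not change. Read as SDs, they pool to 1.68 (pre) or 1.88 (post), and 2.2 becomes d = 1.31 or 1.17. Read as standard errors, they give pooled SDs of 7.2 or 8.2, and d = 0.30 or 0.27. No reading gives 0.9, and 0.75 times any of these SDs is not 1.53 (1.26, 1.41, 5.4 and 6.2 respectively).

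**The case against.** The strongest reply is that two SDs may have been used, for example an SD of change for one figure and an SD of the 12-week value for the other. II.C ties the 0.9 to the previously published study and the 1.53 to the pilot study, and never says outright that these are the same data. In that case neither number is wrong and the fault is an undeclared SD. This possibility stands, but it does not rescue the text. II.C names no second dataset and gives no SD, so the reader cannot get from one figure to the other.

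Other routes to 1.53 were considered:

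- **40 per group at unadjusted two-sided 0.05.** The normal approximation gives 0.6265 × 2.444 = 1.53. This hints that 1.53 may be the slip, but it uses the enrolled number before dropout and no Bonferroni correction, contrary to II.C.
- **A covariate-adjusted SD.** Reducing 2.44 to 2.04 needs a correlation of about 0.55. The planned mixed model in V.A does adjust for baseline and age, so 63% is the power of the t-test in II.C and not of that model. But II.C sizes the trial on a plain t-test and states no correlation.
- **d = 0.9 taken on 12-week values.** Table 1 gives 29.5 − 26.5 = 3.0, hence SD = 3.0/0.9 = 3.33 and a detectable difference of 0.75 × 3.33 = 2.5. That is further from 1.53. It does show that the range 1.66 to 2.03 covers rounding only and assumes that 0.9 belongs to the 2.2.

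It is also fair to say that the practical effect is limited. The sample size does not use 1.53, nor does the −0.8 non-inferiority margin. The link to the yearly review depends on how its benchmark is read. Finally, all of this takes 35 per group as given. Section II.B aims for 20 completers per group, and with 20 the 80%-power effect would be about d = 1.01 (2.47 or 2.06 ml/kg/min on the two SDs). That conflict is a separate matter.

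**Conclusion.** The concern holds. The two pairs of figures in II.C imply SDs of 2.44 and 2.04, and they cannot both follow from one pilot SD. Confidence in the inconsistency is high. Confidence in either corrected figure is not, because the documents do not show whether 0.9 or 1.53 is wrong, or whether an undeclared second SD lies behind them.

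The 1.83 and the 63% hold only if d = 0.9 is correct, refers to the difference in change of 2.2, and uses the same SD as the detectable difference. If 1.53 is correct, the only error is the pilot effect size, which becomes about 1.08. The design itself is not undermined: 35 per group is right for d = 0.75, and power for the full pilot difference is high in both cases. This should be corrected, but it is a reporting error in the stated sensitivity and not a fault in the sample size.

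**What to change.** In II.C, state the pilot SD of VO₂peak in numbers, say whether it is the SD of change or of the 12-week value, and give its source. Then derive both figures from it: pilot d = 2.2/SD, and detectable difference at 35 per group = 0.75 × SD.

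- If d = 0.9 stands on the change difference, restate the detectable difference as about 1.83 ml/kg/min.
- If the SD was 2.04, restate the pilot effect as about d = 1.08.
- If two SDs were used on purpose, give both and say which figure uses which.

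The cost is one SD with its source and one corrected figure. It needs no extra participants and no change to 35 per group. The only downside is that the stated detectable difference may rise from 1.53 to about 1.83.

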- xiv. Aerobic Exercise Intervention: Exercise training will be performed as done previously (13) and will consist of brisk walking and/or slow jogging on a treadmill 5 d each week at approximately 65-75% of each subject's VO₂peak, 45 min/session, at an energy expenditure of 1800-2000 kcal/wk, for 12 weeks. The exercise training will follow a three-stage progression: 1. wk 1=30 min, 3 d/wk, 60% VO₂max; 2. wk 2=30 min, 5 d/wk, 60% VO₂max; and 3. wk 3-12=45 min, 5 d/wk, 60-75% VO₂peak. Exercise intensity for each session will be monitored using heart rate monitors every 5 minutes and at least four exercise sessions per week will be supervised within KUMC exercise facilities.

F. Risk/benefit assessment:

a. Potential risks:

- i. Exercise: Some risks are associated with the exercise testing used to assess maximal aerobic capacity. Cardiovascular events during maximal exercise and in recovery are possible but rare in this population (1). However, these risks could be serious. Therefore, initial screening by maximal stress test will be performed in a clinical setting under the direction of a medical monitor (medical monitor only supervises the graded exercise test). Muscle soreness and strain are possible with exercise testing and training, but these are not a serious risk. The maximal aerobic capacity test represents greater risk of cardiovascular events than the training exercise because of the increased intensity of the exercise. However, events are extremely rare, and subjects will be screened for risk of cardiovascular disease and symptoms. Emergency equipment, including defibrillator, and ambulance plan are available for all subjects. Exercise training will be monitored by trained study staff to reduce risk.

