b. Potential Benefits: All subjects will gain health information about themselves. At the end of the study, results collected will be shared with the subject in face-to-face meetings. Moreover, although we are studying the impact of statins on muscle health, statins overall do have a strong track record of lowering blood lipids and in most trials lowering cardiovascular risk. Moreover, the health information gained throughout the study will aid the subjects in making future medical decisions with their physicians in relation to cardiovascular and diabetes risk. The aerobic exercise intervention will represent a stimulus for the beginning of a permanent improvement in lifestyle and a dramatic reduction in risk of cardiovascular disease.

In summary, the benefits to the subjects are substantial, and the information detailing the impact of statins on mitochondrial, metabolic, and cardiovascular function have the promise of helping millions of patients and physicians evaluate the risk to benefit ratio of statin therapy. There are risks associated with the study, but the experience and medical expertise of the research team should keep these at a minimum, and our track record with exercise and diet research indicates that this diligence has been effective.

G. Location where study will be performed: All portions of the study will occur at KUMC.

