If study staff, tester, or participant reports adverse events or complaints, relevant information will be collected and documented. The participant will be evaluated by the unblinded investigator identified in the protocol. The investigator will determine the severity (according to the CTCAE) and relatedness of the AE to the intervention. The investigator will identify adverse events of clinical concern, those that may require further workup, or suggest that additional participation in the intervention might be a safety risk. These AEs will first be discussed with the participant and then communicated to the study staff or providers with participant's consent and as appropriate. Serious adverse events directly related to study intervention will be reported immediately to the IRB. Any adverse event rate over 30% in 12 mo will be reported to the NIH.

III. Subject Participation

A. Recruitment:

- a.** Subjects will be recruited from the KUMC campus, from hospitals and clinics associated with KUMC and metro-Kansas City, Kansas and Missouri areas. Recruiting will occur through physicians and clinics and through advertisements in emails, flyers, newspaper

ads, radio spots, etc. Interested subjects will call or email and undergo initial phone screening, conducted by trained study staff, to see if they qualify. Should they meet the initial qualifications, they will come to the lab for an informed consent meeting with the PI, research coordinator, or other study staff. They will then be provided with an informed consent that is fully approved by the IRB at KUMC to review prior to the in-person meeting. Subjects who are interested in taking part in the study will be asked to sign the informed consent in the presence of a witness. Participants will have adequate opportunity to review the informed consent and to ask any questions they may have about the research protocol, compensation, risks, and benefits of taking part in the study.

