- b.** The targeted/ planned distribution of subjects by sex/gender and racial/ethnic groups for the proposed study or protocol will follow the local demographics. The Kansas City area has a population that is comprised of 13 % African American, 2% Asian, 5% Hispanic, and 80% Caucasian. It is anticipated that the study population at KUMC will have much the same racial and ethnic make-up. Statistical comparisons among minorities or between minority and Caucasian groups are not aims of the current study. We fully intend to enroll every eligible minority individual in these studies. Ample pools of all targeted populations exist.
- c.** Selection criteria: Only premenopausal women will be included in this study because of the possible complications that hormone replacement therapy may have upon findings. It is anticipated that women will comprise approximately 50% of the study subjects. It is also anticipated that gender will not be a significant factor in the response to exercise training or statin therapy, and hence, it is anticipated that the data from both genders will be compiled and analyzed as a group.
- d.** Exclusions: No minority groups will be excluded.
- e.** Outreach: The subject pool will be limited to the greater Kansas City (MO and KS) area. Subject will need to make regular visits to the laboratories, and thus, subjects will only be recruited who are within the county region and can regularly make appointments.

B. Screening Interview/questionnaire: NA

C. Informed consent process and timing of obtaining of consent: Should the participant meet the initial qualifications, they will come to the lab for an informed consent meeting with the PI, research coordinator, or other study staff. They will be provided with an informed consent that is fully approved by the IRB at KUMC to review prior to the in-person meeting. Subjects who are interested in taking part in the study will be asked to sign the informed consent in the presence of a witness. Participants will have adequate opportunity to review the informed consent and to ask any questions they may have about the research protocol, compensation, risks, and benefits of taking part in the study.

D. Alternatives to Participation: NA

E. Costs to Subjects: There is no cost to subjects for participation in this study.

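### The protocol describes both a two-site and a KUMC-only trial; if two sites enrol, site is in neither the stated randomisation nor the prespecified covariates, at a modest cost in precision

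*Combined protocol and SAP*

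**What the plan says.** Statements that describe two sites:

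- Section II.C (sample size): "The subject enrollment will be split equally between the two sites".
- Section II.H (collaboration) describes a multi-institution project of KUMC and East Carolina University (ECU), with common operating procedures and trial runs at each other's institution.
- Section II.K names a study physician at ECU. Sections II.K and IV.E both provide for discussions at least monthly "to ensure that data collection is occurring in a consistent manner at both locations".
- Section IV.A makes the investigators at both institutions responsible for data quality.

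Statements that describe one site:

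- Section II.G (location): "All portions of the study will occur at KUMC".
- Section II.E, aerobic exercise intervention: "at least four exercise sessions per week will be supervised within KUMC exercise facilities".
- Section III.A, recruitment: "Subjects will be recruited from the KUMC campus, from hospitals and clinics associated with KUMC and metro-Kansas City, Kansas and Missouri areas"; and, under outreach, "The subject pool will be limited to the greater Kansas City (MO and KS) area".
- Section II.I marks single-IRB review for a multi-site study as not applicable.

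On randomisation, section II.C gives only a "computer-based random number generator at a 1:1:1 allocation". No strata or blocks are named. On the model, section V.A says: "For each measure, its baseline measure and age will be added as covariates". It then allows further covariates, such as demographics, BMI and physical activity, as optional additions. Site is not named.

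**The concern.** A reader cannot tell whether one institution or two will supply the sample. That determines what the randomisation and the analysis need.

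If two sites each supply half, the primary outcome (VO2peak after 12 weeks of largely supervised training) is delivered and measured by two teams. A site difference in training response that is neither balanced by design nor modelled goes into the error term and reduces power. The optional-covariate wording in section V.A would permit site, but it leaves that decision until after data are available.

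If only KUMC enrols, there is no site effect, and the equal split in section II.C is wrong as it stands.

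**Working it through.** **Inputs from section II.C.** 35 per group; two-sided two-sample t-test; alpha 0.025 per comparison; effect size d = 0.75; stated power 80%; detectable difference 1.53 ml/kg/min; earlier-study gains of 2.6 and 0.4 ml/kg/min, with an effect size of 0.9.

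**Within-site SD.** Section II.C implies two values: 1.53/0.75 = 2.04, and (2.6 − 0.4)/0.9 = 2.44 ml/kg/min. Both are carried through as a range.

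**Assumed input.** The between-site difference g in VO2peak change is not given. The range taken is 0 to 1 ml/kg/min.

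**Step 1: reproduce the plan's figure.** Noncentral t power with n = 35, d = 0.75 and two-sided alpha 0.025 is 79.9%. The stated 80% reproduces, and it contains no allowance for site.

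**Step 2: ignore site.** With two equal sites differing by g, the variance of the outcome pooled over sites is SD² + g²/4. The SD is therefore inflated by f = √(1 + g²/(4·SD²)), and the effect size becomes 0.75/f.

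| g (ml/kg/min) | f at SD 2.04 | Power | f at SD 2.44 | Power |
|---|---|---|---|---|
| 0 | 1.000 | 79.9% | 1.000 | 79.9% |
| 0.5 | 1.007 | 79.2% | 1.005 | 79.4% |
| 1 | 1.030 | 77.3% | 1.021 | 78.1% |

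Worked line: g = 1, SD = 2.04 gives f = √(1 + 1/(4 × 4.16)) = √1.060 = 1.030; d = 0.75/1.030 = 0.728; power 77.3%.

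**Step 3: chance imbalance.** With unstratified allocation and 35 per arm, the difference in site share between two arms has SD √(0.25 × 2/35) = 0.12, or 12 percentage points. A permutation simulation gives the same SD, and a 12% chance of a gap of 20 points or more. At g = 1 this moves the arm contrast with SD 1 × 0.12 = 0.12 ml/kg/min. At SD 2.04 the standard error of the contrast without a site effect is 2.04 × √(2/35) = 0.488. Adding the site component gives √(0.488² + 0.12²) = 0.502, and 0.502/0.488 = 1.03, which is the f of step 2. Imbalance and the wider error term are thus one variance component.

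**Step 4: type I error and the remedy.** These are simulations with 8,000 runs per cell and site gaps of 0, 0.5 and 1.0 within-site SD.

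- Unstratified allocation, site omitted: type I error 0.022 to 0.028 against 0.025 (20 or 35 per group), so there is no systematic bias.
- Site in the model, 35 per group: power about 79% with unstratified and about 80% with stratified allocation, at every gap.
- Stratified allocation but site left out of the model, gap 1.0 SD: type I error 0.0125 (35 per group) and 0.014 (20 per group), so the test is conservative. Stratification and adjustment belong together.

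**The case against.** **The local-protocol reading.** References to the KUMC review board and the study population at KUMC, beside an ECU investigator and physician, fit KUMC's own document for a two-site trial. The single-site statements would then be local ones and the contradiction largely disappears. This is plausible, but the text does not say so. On this reading two sites do enrol and the omission of site from the plan remains.

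**Mitigation.** Common operating procedures, reciprocal trial runs and monthly discussions should narrow any gap. Baseline adjustment absorbs much of a stable difference in equipment or calibration. This stands as a limit on size. Neither removes a site difference in training response or drift in measurement.

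**Silence is not exclusion.** Section II.C does not rule out strata, and section V.A permits extra covariates. That is correct; the point is that site is not prespecified.

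**Stronger readings that a reader might infer.**

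- *Much larger power losses.* A gap of 2 ml/kg/min gives 70% to 73%, and 3 gives about 59% to 65%. But 2 is 77% of the whole 2.6 ml/kg/min training response in the earlier study, and 3 exceeds it. Nothing in the documents supports gaps of that size.
- *Imbalance as a second harm.* Step 3 shows that it is already counted in the power loss.
- *Half the sample does not exist, so power is about 52% (20 per arm) or 47% (18 per arm).* These figures compute correctly, but they assume that a KUMC-only trial would enrol just half of 120. The documents do not say that. Section II.B has its own plan of at most 80 randomised and 60 completers, which conflicts with the 105 and 120 of section II.C. That conflict is a separate point.

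**Conclusion.** The site statements contradict each other in current text and need to be reconciled. If two sites enrol, site should be in both the randomisation and the prespecified model, and at present it is in neither.

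The statistical cost is modest: at 35 per group, power falls by less than one percentage point at an assumed gap of 0.5 ml/kg/min and by about two to three points at 1 ml/kg/min. This rests on an assumed gap, two equal sites, d held at 0.75, a within-site SD of 2.04 to 2.44, and the plan's own unadjusted t-test. It is a loss of precision only; type I error stays near nominal. If the trial is KUMC-only, this cost is zero and the correction is to the text and the stated numbers.

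**What to change.** State in sections II.C, II.G, II.H and III.A how many sites enrol and what each one does. If this is the KUMC local protocol of a two-site trial, say so.

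- **If two sites enrol:** randomise 1:1:1 in permuted blocks within site, and name site in section V.A as a fixed effect beside the baseline value and age. Make both changes together. The cost is a stratified list and one degree of freedom, with no extra participants or procedures.
- **If KUMC is the only site:** delete the two-site split and the references to data collection at both locations, and make the stated sample size match what KUMC will enrol. The cost is a text amendment, with power restated if the number changes.
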